For patients assigned to the “Fast Track” arm, the Fast Track clinic supervisor will schedule an appointment for the patient with an ACP. For patients assigned to the standard treatment arm, the booking clerk will schedule an appointment for the patient with a sleep physician. Patients will be asked to arrive 15 - 20 minutes prior to the appointment to complete study questionnaires. The booking clerks will notify the RA of the initial appointment date and time.

STUDY PROCEDURE

BASELINE VISIT & TREATMENT PLAN

When patient arrives, the RA will ask the patients to complete the following questionnaires (ESS, Short SAQLI without treatment section, and HUI). The study will require an ESS at the time of the baseline visit, even though there may be multiple ESS questionnaires in the patient's chart.

If required, the sleep physician will order a polysomnography (PSG). The RA will check that the PSG is ordered as "urgent". The following will be collected: PSG date, AHI, mean oxygen saturation and percentage of time under 90%.

The RA will access the CPAP database to retrieve the patient's treatment type. The RA will retrieve the patient's treatment start date for the following treatments by:

- CPAP/BAP – retrieving and calling the homecare company OR CPAP database,
- Oxygen only – looking at the patient's chart for the date when the patient was contacted about the PSG results (if the patient is previously on oxygen) OR determining when the patient started on oxygen,
- Dental appliance – calling the dentist,
- Weight loss – looking in the patient's chart for the date treatment options were offered

Possible scenarios	Action
Patient cancels or does not show to the appointment	The RA will note the original appointment date and the rescheduled date.
Patient does not show for 3 or more appointments	Patient is discharged from the CPAP clinic and the study.
Patient stops their initial treatment	The RA will note new treatment. 3-month and 1-year appointments will still be based on the original treatment date.
Multiple patients need to meet the RA at the same time (recruitment, clinical visits)	Possible options: 
 1) Ask an another RA to assist in one of the appointments 2) Ask The Fast Track clinic supervisor to obtain clinical study data at visit

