Patients with only a verbal consent to the study	The RA will review the study with the patient and obtain a written consent to the patient regardless if the patient is eligible or not. 
If the patient revokes their verbal consent, the RA will remove patient from the study, identify the reason why the patient does not want to participate in the study. Because the patient has not yet had an initial appointment with a physician or an ACP, the patient will not be counted as part of the 150 patients recruited.
 
The RA will notify the Fast Track clinic supervisor of patient.

Patient delays their treatment	If the patient delays their treatment due to insurance purposes, treatment start date will be the date they start their treatment. 
If the patient delays their treatment due to other medical reasons, the treatment start date will be the date that treatment was offered. Three-month and one year follow-up data will be collected as per usual procedures.

Patient has had multiple PSGs after the indicated treatment start date	The RA will pull the file and review with the LSP as the treatment start date may need to be modified.
Patient does not have sleep disordered breathing after further testing (e.g., PSG)	The treatment start date will be the date of the diagnostic test. Three-month and one year follow-up data will be collected as per usual procedures.

3-MONTH & 1-YEAR FOLLOW-UP (\pm 2 WEEKS)

3-Month Appointment Date and Time

The RA will create a list (weekly) of patients who have completed their initial appointment for the booking clerk. The booking clerk will review the scheduling system to book and/or confirm patient's 3-month appointment. Upon receiving the appointment date, the RA will complete a HSAT requisition for the booking clerk to book patient for a HSAT (in-house or with the patient's CPAP company – if ordering a HSAT from the home care provider, state on cover letter to send the raw data to FMC Sleep Centre) on the day of the follow-up appointment or whenever is most convenient for the patient. HSAT test is to be completed with a Remmers recorder. Note: if the patient is on O2, request the HSAT done on room air or without O2. If the HSAT is completed on O2 note make a note that it was completed on O2 on the patients chart.

1-Year Appointment Date and Time

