The RA will create a list (every 3 months) of patients who have completed their 3-month follow-up appointment for the booking clerk. The booking clerk will create a tracking task in the scheduling system to book the appointment several months before the 1-year target date. When the appointment is book, booking clerk will notify RA of appointment date and time. Upon receiving the appointment date, RA will complete a HSAT requisition for the booking clerk to book patient for a HSAT (in-house or with the patient's CPAP company) on the day of the follow-up appointment or whenever is most convenient for the patient. HSAT test is to be completed with a Remmers recorder.

The RA will attempt to call all three month and one year patients who do not have a follow up appointment booked through the Sleep Centre to coordinate the best date and time to complete the questionnaires.

If the patient does not have a follow-up appointment booked at the Sleep Centre. We will use the date that the patient returns their questionnaire as the final appointment date; however, the research associate should note that it is the follow-up date not the final appointment date.

At Time of Appointment

The RA will give the patient a questionnaire package (ESS, Short SAQLI including treatment section, HUI, VSQ-9) at the time of visit. The ESS, Short SAQLI including treatment section and the HUI surveys are to be completed before the patient enters the clinical appointment. The VSQ9 survey is

to be completed after the patient completes their clinical appointment. Download data will be obtained by the Fast Track clinic supervisor or by the therapist. The patient will not be compensated for parking if the follow-up visit is part of the patient's clinical care.

If there are any information missing from the Fast Track Summary sheet (i.e. Triaging criteria, co-morbidities or medication), the RA will retrieve them from the chart or from the CPAP database before/during the time of visit.

Possible scenarios	Action

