Patient has a follow-up appointment booked outside of the 3-month or 1-year period	
The RA will book a follow-up appointment outside of the CPAP clinic with the patient and provide a reminder phone call a week before the appointment. The RA will also book a HSAT as per normal procedure.
 
At the appointment, the RA will:
 
 1. Ask patient to complete the questionnaire package 2. Ask The Fast Track clinic supervisor or the home-care company to retrieve CPAP data from the patient's machine 3. Give the patient a pre-paid parking voucher.
Patient cannot come in for a follow-up appointment.	
The RA will book a HSAT via home-care company.
 
The RA will email, fax, OR book a phone appointment with the patient to complete the questionnaire package. The date that the patient returns their questionnaire will be considered the final appointment date (3-month and 1-year); however, the RA should note that it is the follow-up date not the final appointment date.
 
The RA will phone the home-care company to retrieve CPAP data from the patient's machine.

HSAT cannot be booked on the same day as the 3 month or 1 year follow-up appointment.	The booking clerk will book a HSAT closest date to the follow-up appointment. The RA will give the patient a pre-paid parking voucher if the test was not ordered as part of the patient's clinical care.
Patient randomized in the "Fast Track" treatment arm requests to be seen by a physician.	
The RA will confirm that participant still wishes to participate in the study. If so, then the patient will remain in the assigned study arm (as per the modified intention to treat design), and physician visits will be tracked as per study outcomes.
 
If the participant requests to withdraw from the study and withdraws from having their health utilization data collected, then no further research data will be collected. The patient will be informed that we will not collect questionnaires, additional clinical and HC utilization/cost data. Data up to the point of withdrawal is accessible to the research team. Everything else will be the same in terms of clinical care (i.e. dropping out of the Fast Track arm doesn't necessarily mean that all subsequent visits are with a physician, but rather that the patient goes back into standard care – physician-led but with heavy ACP involvement)

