	Partial pressure of CO2 on ABG	Netcare – will need to ask a person with access to Netcare (The Fast Track clinic supervisor or [name])	Photocopy
	HSAT Date	Chart	Handwritten
Baseline Visit	Initial baseline visit date	Sleep clinic's CIS system.	Handwritten
	Actual baseline visit date		
	ESS	At baseline visit.	Original
	Health Utilities Index		
	Short SAQLI (without treatment section)		
	Current medications	Patient's chart: 1) Patient info sheet (yellow) when patient comes in for the HSAT, 2) Physician's initial visit letter 3) Patient's self-filled questionnaire, 4) Administrative data from AHS	Handwritten
	Comorbidities		
	PSG date (if applicable)	Sleep clinic's CIS system.	Handwritten
	PSG - AHI, mean O2 saturation, time under 90%	Patient's chart - PSG report	Handwritten
	Treatment start date	CPAP database, homecare company (CPAP/BAP), patient's chart (Oxygen), dentist (dental appliance)	Handwritten
	Treatment type	CPAP database	Handwritten

	Data to collect	Data source	Photocopy, handwritten or original copy
3-Month/1-Year Follow-up	Initial 3-month/1-year visit date	Sleep clinic's CIS system. At 3-month and 1-year visit.	Handwritten
	Actual 3-month/1-year visit date		
	ESS		Original copy
	Health Utilities Index		
	Short SAQLI (with treatment section)		
	Positive airway pressure adherence (1 month directly prior to the appointment) & date		Photocopy
1-Year only	Healthcare utilization - cumulative sum of outpatient physician visits, hospitalizations and length of stay, and urgent care/emergency room visits	DIMR Database	Electronic copy
	Healthcare utilization – additional physician consultation time	Patient's chart: Written communication between ACPs and physicians are recorded on a yellow sheet.	Photocopy
	Healthcare costs – costs for sleep physician and ACP visit, diagnostic sleep testing costs for HSAT and PSG	Taken from the Alberta Health Schedule of Medical Benefits, Health Sciences Association of Alberta (HSAA) Collective Agreement and the FMC sleep Sleep Centre Medical Director	Electronic copy
	Healthcare costs – CPAP therapy costs	Current market pricing through respiratory homecare providers	Electronic copy
	Healthcare costs – hospitalization costs	DIMR and AHS Finance department	Electronic copy
	Healthcare costs – costs for ambulatory visits	Canadian Institute for Health Information (CIHI) and DIMR	Electronic copy

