Evaluation of a “Fast Track” Respiratory Therapy Clinic for Patients with Suspected Severe Sleep-Disordered Breathing

STATISTICAL ANALYSIS PLAN

NCT#: 02191085

Document Date: February 16, 2017

Evaluation of a "Fast Track" Respiratory Therapy Clinic for Patients With Suspected Severe Sleep-Disordered Breathing

Statistical Analysis

This study will use a modified intention to treat analysis, in which results will be analyzed for patients who are randomized and have treatment adherence data three months after initiating PAP therapy.

Paired t tests will be used to compare clinical outcomes from baseline to 3 months and one year and unpaired t tests will be used to compare time to treatment initiation and measures of patient demand. Multiple logistic regression will be used to identify predictors of study outcomes using variables identified as predictive on univariate regression. Outcomes will be transformed into binary variables based on clinically relevant cut-offs.

The economic analysis will be performed using the perspective of a publicly funded healthcare system. An estimate of mean utility scores based on the HUI questionnaire will be calculated and the average quality-adjusted life- year (QALY) will be calculated for each study arm. Using bootstrapping, we will compare the difference in mean costs and QALYs between the study arms to generate an incremental cost-effectiveness ratio for an ACP-led clinic compared to traditional physician-led care. Sensitivity analyses will be performed to evaluate the effect of changes in physician fees, RT salaries, diagnostic testing costs and treatment costs.

All study outcomes will be analyzed in different subgroups to clarify the impact of ACP-led care for patients with different patient flow pathways or clinical treatments. Pre-specified subgroups include:

- Patients who undergo PSG vs. patients who do not undergo PSG
- Patients treated with bilevel PAP vs. patients treated with CPAP
- Patients who are treated with oxygen vs. patients treated without oxygen

Sample Size

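### Three-month PAP adherence, the powered endpoint, is tied to the appointment rather than to a fixed period of days after PAP start, and neither document says how late or mis-anchored downloads are handled

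*Protocol*

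**What the plan says.** The SAP's Statistical Analysis section limits the analysis to randomised patients who "have treatment adherence data three months after initiating PAP therapy". Its Sample Size section powers the trial on PAP adherence with a margin of 1 hour, and continues recruitment until 150 patients have three-month adherence data. It gives no day range for the adherence average.

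The operational definition is in the protocol's Data Collection table, under 3-Month/1-Year Follow-up: "Positive airway pressure adherence (1 month directly prior to the appointment) & date". The Appendix 1 summary sheet says only that adherence covers one month.

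Three protocol rules hold the appointment near its target:
- The follow-up section is headed with a tolerance of ±2 weeks.
- If a patient stops the initial treatment, "3-month and 1-year appointments will still be based on the original treatment date" (Baseline Visit & Treatment Plan, scenarios).
- If the clinic appointment falls outside the 3-month or 1-year period, "The RA will book a follow-up appointment outside of the CPAP clinic with the patient" (follow-up scenarios).

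Other rules loosen it:
- If no Sleep Centre follow-up is booked, "We will use the date that the patient returns their questionnaire as the final appointment date".
- If the patient cannot come in, "The date that the patient returns their questionnaire will be considered the final appointment date (3-month and 1-year"). A similar rule covers patients without a clinical follow-up at 3 or 12 months. In each case the research associate must also note that this is a follow-up date and not the final appointment date.
- If treatment is delayed for medical reasons other than insurance, "the treatment start date will be the date that treatment was offered".

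**The concern.** The SAP describes a time on treatment, whereas the data table describes a period ending at an appointment. The two agree only if the appointment falls at the same time after PAP start for every patient. If adherence changes over the first months, patients measured at different times contribute different quantities. If that timing also differed between arms, part of the difference compared with the 1 h margin would reflect timing and not model of care.

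A second issue does not depend on drift. The modified intention-to-treat set and the end of recruitment both depend on what counts as three-month data. With no window rule in the SAP, whether a late download qualifies would be decided patient by patient. The research associate who assigns the arms also books the out-of-period study visits, so such decisions could be made with the arm known.

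**Working it through.** **1. The plan's own figure.** Inputs from the SAP's Sample Size section: margin 1 h, SD 2 h, power 90%, type I error 0.05 (sidedness not stated).

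n per arm = 2 × SD² × (z_α + z_β)² / margin² = 2 × 4 × (1.645 + 1.282)² / 1² = 68.5, rounded up to 69, or 138 in total. This reproduces the SAP with a one-sided 0.05. A one-sided 0.025 gives 85 per arm (170), which does not match. Power at 69 per arm is 90.2%.

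**2. Spread of the measurement month inside the tolerance.** Take three months as 91 days and the month as 30 days.
- Earliest visit: 91 − 14 = day 77, so the month is days 47-77.
- Latest visit: 91 + 14 = day 105, so the month is days 75-105.

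The two months share only days 75-77.

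**3. Where the tolerance may not hold.** A patient who cannot be reached is called weekly for a month and then sent a letter (follow-up scenarios), which already takes longer than the two-week tolerance. The questionnaire-return rules set no limit on lateness, and the provider download request has no stated date range.

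**4. Start-date mismatch.** If treatment start is the date of the offer and PAP begins d days later, a visit at day 91 measures days (61 − d) to (91 − d) on PAP. As an illustration, d = 30 gives days 31-61. A delay beyond 61 days would put part of the month before PAP had begun.

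**5. Timing variation equal in both arms.** Assume adherence drifts 0.1-0.3 h per month and visits are spread uniformly over ±14 days (±0.46 month). The added SD is drift × 0.46/√3 = 0.03-0.08 h. The total SD is √(4 + added SD²) = 2.000-2.002 h, and n stays at 69.

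**6. Timing that differs by arm.** SE = 2 × √(2/69) = 0.3405 h. Bias = drift × mean gap between arms. If the bias favours the ACP arm, one-sided error at the margin = 1 − Φ(1.645 − bias/SE). If it runs against that arm and the true difference is zero, power = Φ((1 − bias)/SE − 1.645). Drift and gap are assumptions; the documents give neither.

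| Mean gap between arms | Drift (h/month) | Bias (h) | One-sided error | Power if reversed |
|---|---|---|---|---|
| 1 week (0.23 month) | 0.1 | 0.02 | 5.7% | 89.0% |
| 1 week | 0.3 | 0.07 | 7.5% | 86.2% |
| 28 days (0.92 month), the limit under ±2 weeks | 0.1 | 0.09 | 8.5% | 84.6% |
| 28 days | 0.3 | 0.28 | 20.2% | 68.5% |
| 2 months (late data in one arm) | 0.1 | 0.20 | 14.5% | 75.9% |

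The 28-day rows require every patient in one arm to be at the earliest limit and every patient in the other at the latest. They are a ceiling, not an expectation.

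**The case against.** The strongest reply is that the plan does aim at time on treatment. Follow-up carries a ±2-week tolerance, is counted from the treatment date, and an out-of-period clinic visit triggers a separate study visit at which CPAP data are retrieved. The row on patients without a 3- or 12-month clinical follow-up is a remedy for mistimed visits, not permission for them. All of this stands: the month does not float freely with whichever appointment happens to occur.

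The questionnaire-return rule can also be read more narrowly. The protocol has the return date flagged as a follow-up date, handles downloads separately, and nowhere says that the adherence month is counted back from the return. That link is an inference. It remains the natural reading because the month is defined by the appointment and no other anchor is given for patients who are not seen.

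A reader might infer that timing differs by arm, because the protocol says appointment availability depends on the randomised arm. That statement concerns the initial provider appointment. Follow-up booking is described once for both arms and counted from treatment start, so faster initial access does not by itself shift the month. A reader might also infer an error rate of 9-22%. That follows from a bias of 0.1-0.3 h, which at this drift needs a full month's mean gap between arms, more than ±2 weeks allows.

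Finally, timing can be checked afterwards, since the adherence date, treatment date and appointment dates are all recorded. That allows a check of the problem but does not define the endpoint in advance.

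**Conclusion.** The point holds as an incompletely defined powered endpoint, not as a demonstrated bias. The adherence month is tied to the appointment, can shift by 28 days within tolerance, has no stated limit when a questionnaire return replaces the visit, and may be counted from an offer date that does not match the SAP's reference to starting PAP. The protocol's treatment-start rules and the SAP wording must be reconciled.

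The size is probably modest. Variation common to both arms does not matter. A one-week gap between arms costs at most a few percentage points of error or power under the assumed 0.1-0.3 h per month drift. Materially larger effects need either a near-complete separation of the arms inside the tolerance or out-of-window data that differ by arm, and the documents show neither. The change is still worth making because it removes a possible timing bias and a patient-by-patient judgement about which data qualify, at little cost.

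**What to change.** In the SAP, define three-month and one-year adherence as mean nightly use over a fixed day range counted from actual PAP start (for example days 61-90, and the last 30 days of year one), taken from the device download whatever the visit or questionnaire date. In addition:
- Ask the clinic or PAP provider for that date range in every download request.
- State what happens when a download does not cover the range, and whether that patient counts as having three-month data for the analysis set and the 150-patient target.
- For the adherence endpoint, reconcile the protocol's offer-date rule with the SAP's reference to PAP initiation.
- Keep the appointment-anchored month as a sensitivity analysis, and report download timing by arm.

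This adds no visit and leaves the sample size at 138. The costs are a date range added to the download request and the likelihood that a few downloads will not cover it.

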Evaluation of a “Fast Track” Respiratory Therapy Clinic for Patients with Suspected Severe Sleep-Disordered Breathing

STATISTICAL ANALYSIS PLAN

NCT#: 02191085

Document Date: February 16, 2017

Evaluation of a "Fast Track" Respiratory Therapy Clinic for Patients With Suspected Severe Sleep-Disordered Breathing

Statistical Analysis

This study will use a modified intention to treat analysis, in which results will be analyzed for patients who are randomized and have treatment adherence data three months after initiating PAP therapy.

Paired t tests will be used to compare clinical outcomes from baseline to 3 months and one year and unpaired t tests will be used to compare time to treatment initiation and measures of patient demand. Multiple logistic regression will be used to identify predictors of study outcomes using variables identified as predictive on univariate regression. Outcomes will be transformed into binary variables based on clinically relevant cut-offs.

The economic analysis will be performed using the perspective of a publicly funded healthcare system. An estimate of mean utility scores based on the HUI questionnaire will be calculated and the average quality-adjusted life- year (QALY) will be calculated for each study arm. Using bootstrapping, we will compare the difference in mean costs and QALYs between the study arms to generate an incremental cost-effectiveness ratio for an ACP-led clinic compared to traditional physician-led care. Sensitivity analyses will be performed to evaluate the effect of changes in physician fees, RT salaries, diagnostic testing costs and treatment costs.

All study outcomes will be analyzed in different subgroups to clarify the impact of ACP-led care for patients with different patient flow pathways or clinical treatments. Pre-specified subgroups include:

- Patients who undergo PSG vs. patients who do not undergo PSG
- Patients treated with bilevel PAP vs. patients treated with CPAP
- Patients who are treated with oxygen vs. patients treated without oxygen

Sample Size

The study is powered to assess the non-inferiority of ACP-led care compared to usual care by sleep physicians. A non-inferiority margin of -1 hour of PAP adherence was determined by consensus of the investigators and has been used in previous studies comparing different models of care for SDB. One hundred thirty eight patients (69 in each arm) will be required to achieve 90% power with a type I error of 0.05, using this non-inferiority margin and a standard deviation of 2 hours of nightly CPAP use. The standard deviation used in the sample size calculation was based upon the results of two previous studies. To account for withdrawals and loss to follow-up (approximately 15% at the FMC Sleep Centre), recruitment will continue until three-month adherence data is available for 150 patients.

Reference: Ip-Buting A, Kelly J, Santana MJ, Penz ED, Flemons WW, Tsai WH, et al.

Evaluation of an alternative care provider clinic for severe sleep-disordered breathing: a study protocol for a randomised controlled trial. *BMJ Open*. 2017 Mar;7(3):e014012.

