Patient cannot stay after HSAT training to complete the consenting process	
The RA will provide the following options to the patient:
 
 1) Explain and obtain a verbal consent over the phone, followed by a written consent at the baseline visit (regardless of eligibility),

	
2) Explain and obtain written consent when patient returns the HSAT machine, 3) Give the consent form to the patient to read/sign at home and return when patient returns the machine.
 
If patient refuses all options, patient is opted out of the study. The RA will notify the Fast Track clinic supervisor of patient and tally the number and reason of non-consenting patients.
 
The LSP will review all charts with the Fast Track clinic supervisor to determine if the assessment will be done with the ACP Fast Track clinic (non-study) or by a sleep physician.

Patient expresses difficulty in availability	
The RA will let patients know that the questionnaire portion of the study could be mailed/mailed to the patient and HSAT could be completed via homecare company.
 
If patient still expresses difficulty, the RA will check if the patient would rather opt out of the study.

Patient requires more time to understand and read through the consent form.	
The patient will be given a consent form to take home and return after completing the ambulatory sleep test. If a consent form is not returned within 24 hours, the RA will call to follow-up with the patient.

Patients who are eligible based on previous HSAT results	
The Fast Track clinic supervisor will contact the patients via phone to obtain verbal consent for general research. If patient provides verbal consent, the Fast Track clinic supervisor will introduce the study and inform that an RA will be contact the patient. The RA will call the patient for a verbal consent for the study. If patient provides a verbal consent, a written consent will be obtained during the patient's baseline visit regardless of eligibility.

Note: Unlike standard referral procedures, the ambulatory sleep test and provider appointment will not be scheduled simultaneously, since the assignment of provider and subsequent appointment availability will depend on the study arm to which the patient is randomized.

ELIGIBILITY

Eligibility criteria include:

- Written consent signed by the patient,
- Patient is over 18 years old,
- Patient did not have previous treatment of SDB,

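### The only analysis set depends on events after randomisation; no all-randomised or missing-data analysis of adherence is planned, and the set for time to treatment, costs and QALYs is ambiguous

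*SAP*

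**What the plan says.** SAP, Statistical Analysis, opens with a modified intention-to-treat rule: "results will be analyzed for patients who are randomized and have treatment adherence data three months after initiating PAP therapy". No other population is named. Time to treatment is handled in one clause, "unpaired t tests will be used to compare time to treatment initiation and measures of patient demand", and costs and QALYs are compared by study arm using bootstrapping. The only sensitivity analyses vary fees, salaries, testing costs and treatment costs. SAP, Sample Size, keeps recruitment open until 150 patients have three-month adherence data, and gives one pooled figure of about 15% for withdrawal and loss.

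The protocol collects data on randomised patients who may have no PAP download:

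- Baseline Visit & Treatment Plan gives start-date rules for oxygen alone ("OR determining when the patient started on oxygen" is one of the two routes), for dental appliances and for weight loss ("chart for the date treatment options were offered").
- For patients found not to have sleep-disordered breathing (SDB) it says "The treatment start date will be the date of the diagnostic test", and they remain in follow-up.
- Data Collection plans one-year utilisation: "cumulative sum of outpatient physician visits, hospitalizations and length of stay, and urgent care/emergency room visits".

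Several rules limit loss. A patient who stops treatment keeps the original follow-up timing. A Fast Track patient who asks for a physician stays in the assigned arm. A patient discharged by the clinic is approached to continue, and missing downloads are chased through the PAP provider. On the other side, three or more missed appointments end study participation, and a patient without a baseline visit is not counted in the study.

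**The concern.** The trial compares two ways of delivering care. Randomisation makes the arms comparable at allocation, but the analysis set is formed later, from patients who started PAP and produced a three-month download. The note in the Consenting Process section says that "subsequent appointment availability will depend on the study arm to which the patient is randomized", so the wait for a first visit, and with it the chance of dropping out beforehand, could differ by arm. If it does, the analysed groups are no longer the randomised groups. Recruiting on to 150 patients with data restores the numbers but not the comparability.

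For adherence, the bias can run either way. If the ACP arm loses more non-users, a worse clinic can look acceptable; if the physician arm does, an equal clinic can fail. With no second analysis planned, a reader could not tell which had happened.

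For time to treatment, costs and QALYs, the question is who is counted. If the set applies to them too, the results describe PAP patients with downloads and not everyone sent to each clinic.

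**Working it through.** **1. The plan's own figure.** SAP inputs: margin 1 h, SD 2 h, power 90%, type I error 0.05. With a one-sided 0.05 (the side is not stated):

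n per arm = 2 × 2² × (1.645 + 1.282)² / 1² = 68.5, so 69 per arm and 138 in total, as stated. One-sided 0.025 would need 85 per arm. The sample size is not at issue here.

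**2. How many are left out.** At 15% loss, 150 / 0.85 gives about 177 randomised, so about 27 fall outside the only defined set.

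**3. Adherence, ACP clinic truly 1 h worse.** Assumptions not in the documents: PAP users in the physician arm average m = 4, 5 or 6 h, SD 2 h; excluded patients use 0 h; the true difference of -1 h is a mean over all randomised patients; loss is L_A (ACP) and L_P (physician).

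- ACP user mean = [(1 - L_P)m - 1] / (1 - L_A)
- Modified ITT difference d = ACP user mean - m
- Probability of declaring non-inferiority = Φ((d + 1)/SE - 1.645)

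For 20% v 10%, the 150 observed patients split as 150 × 0.8/1.7 = 70.6 and 150 × 0.9/1.7 = 79.4, so SE = 2√(1/70.6 + 1/79.4) = 0.327. For m = 4, ACP user mean = (3.6 - 1)/0.8 = 3.25, d = -0.75, and Φ(0.25/0.327 - 1.645) = 0.19. The other cases follow in the same way:

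| Loss, ACP v physician | d at m = 4/5/6 | Non-inferiority declared |
|---|---|---|
| 20% v 10% | -0.75/-0.625/-0.50 | 19/31/45% |
| 17.5% v 12.5% | -0.97/-0.91/-0.85 | 6/9/12% |
| 15% v 15% | -1.18 (all m) | 1.4% |

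If only half of the excluded patients use 0 h and the rest use PAP like others in their arm, 20% v 10% gives 10/13/17%. A simulation that recruits until 150 have data agrees with the first row to within about one percentage point.

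**4. Loss reversed (10% v 20%), no true difference.** ACP user mean = 0.8m/0.9, so d = -0.44/-0.56/-0.67, and non-inferiority is declared in about 52/39/27% of trials. The planned power with 75 per arm is 92%.

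**5. Time to treatment.** Assumptions: exponential waits with mean T, and the same constant leaving rate u in both arms. Loss = uT/(1 + uT), and mean wait among the treated = T/(1 + uT). Setting the shorter wait to T = 1, a true ratio r appears as r(1 + u)/(1 + ru). With a two-fold wait and 15% pooled loss, u = 0.1197. Loss is then 10.7% v 19.3%, and the ratio appears as 2 × 1.1197/1.2393 = 1.81. If only half of that loss (7.5%) occurs while waiting, u = 0.0545 and the ratio appears as 1.90.

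**The case against.** **The error rates answer a different question from the SAP's.** The SAP sets its margin and SD for nightly CPAP use and analyses patients with data. Among them, the assumed differences of -0.75 to -0.50 h lie inside the margin, so declaring non-inferiority is correct for that target. This stands. A reader might infer that the planned test has a 19 to 45% error rate; the documents do not support that. The figures hold only if the margin is applied to all randomised patients and loss is uneven.

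**Uneven loss is assumed.** The protocol says that appointment availability depends on arm, not that loss does. This also stands, and at equal loss the error is below nominal.

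**The excluded group is narrow.** A reader might infer that everyone who stops treatment, asks for a physician or is discharged drops out. The protocol keeps these patients in follow-up. The clearly excluded are those who never start PAP and those whose download cannot be retrieved.

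**The SAP does not expressly confine costs, QALYs or time to treatment to PAP patients.** A reader might infer that it does. The economic paragraph speaks of study arms, and the protocol collects the wider data. The oxygen subgroup ("Patients who are treated with oxygen vs. patients treated without oxygen") settles nothing, because patients on PAP plus oxygen could fill it. The point is therefore one of ambiguity. Nor is every untreated patient without a date: weight-loss, medically delayed and no-SDB patients are assigned one. Only those with no date at all have no place in a t test.

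**Patients who revoke verbal consent** could not count towards 150 with three-month data in any case, and written consent is an eligibility criterion. What remains is a reporting matter.

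**Conclusion.** The gap for adherence is clear: one analysis set, formed after randomisation, with no planned analysis that would reveal bias from uneven loss. Its size cannot be known in advance. It is negligible as a source of false non-inferiority if loss, and use among those lost, are equal across arms. It is modest at a five-point gap in loss and large at a ten-point gap, on the assumptions of 4 to 6 h mean use, excluded patients at 0 h, and a margin applied to all randomised patients. The direction is open.

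For time to treatment, costs and QALYs, the conclusion is that the population must be stated, not that the wrong one has been chosen. Under the exponential model, a two-fold wait would appear as about 1.8 to 1.9-fold, so the direction and rough size survive.

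This should be fixed. It does not invalidate the primary analysis or the sample size.

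**What to change.** 1. **State the population for each outcome.** Analyse time to treatment, costs and QALYs in all randomised consenting patients by assigned arm. Use a time-to-event method for time to treatment, applying the protocol's start-date rules and censoring patients who never start at withdrawal or last follow-up. Use multiple imputation for missing HUI.
2. **Keep the modified ITT adherence analysis and add one pre-specified sensitivity analysis** in all randomised patients prescribed PAP. Use 0 h for those known not to have started, actual downloads for stoppers where available, and multiple imputation with a tipping point for unknown downloads. Report patients with no SDB or non-PAP treatment separately by arm; do not score them 0 h, since not needing PAP is not poor adherence.
3. **Interpret disagreement by the estimates and the tipping point**, with no automatic label of non-robustness. In simulation with no true difference, 15% loss in each arm and all excluded at 0 h, modified ITT showed non-inferiority while the zero-score analysis did not in about 6/12/19% of trials at 4/5/6 h.
4. **Report exclusions by arm and reason**, including randomised patients without a baseline visit. This is a minor reporting point, with data used only where consent allows.

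The cost is SAP wording and more analysis work; most of the data are already collected and the required number does not change. The sensitivity analysis has lower power. In the worst case, with all excluded at 0 h, 15% loss and 88 per arm, the SD is √(0.85 × 4 + 0.15 × 0.85 × m²) = 2.33/2.57/2.83 h. Power is then about 88/82/76%, against about 92% for modified ITT.
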